We will consider factors that must be in place to initiate and sustain first time blood donors' attempts at returning to donate blood. These are called predisposing, enabling and reinforcing factors. We will identify these factors through analysis of primary and secondary data, and put them into categories, and rank their importance.

Predisposing factors, which explain first-time blood donors' behaviour regarding subsequent donation efforts, include knowledge, attitudes, cultural beliefs, and readiness to change. Enabling factors, which enable first-time blood donors to act on their beliefs, attitudes, and knowledge, include the availability of policies, assistance, or resources.

Reinforcing factors, which become prominent after a behaviour has been started, promote repetition or persistence of behaviour through the provision of continuing rewards or incentives such as praise or reassurance.

These factors will be identified from previous data on first-time blood donors in Ghana, and the key informant interviews with participants will be drawn from the NBSG staff, community-based blood donation volunteers, blood donors and non-blood donors.

Phase 5: Administrative and Policy Assessment

Identify the administrative and policy factors that influence what can be implemented. The team will evaluate how organizational factors such as policies, procedures, culture and the availability of resources influence what can be implemented by using two approaches to evaluate implementation research outcomes of the interventions. These are the creation of WhatsApp and docu-drama interventions and test-running the interventions.

WhatsApp pilot RCT

A WhatsApp group will be formed for the pilot RCT. There will be one study team member, who will be the content mediator (research assistant), and who will be responsible for sending

weekly messages and clarifications on blood donation for six months. The participants in the WhatsApp group, after the pilot RCT will have a focus group discussion on what worked well and what did not, and provide information on feasibility, acceptability and cultural appropriateness of the intervention. Prior to, and after exposure to the WhatsApp intervention, a pre-, and post-test survey on the theory of planned behaviour constructs and implementation research measures will be conducted.

Docu-drama test-run

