and varying block sizes) stratified by blood donor type. Computer-generated random intervention assignments will be generated by an independent study statistician and conveyed electronically through a web-based app at the time of enrollment to preserve allocation concealment. The upcoming intervention assignment will be concealed from the study staff prior to the randomization outcome. Details on randomization are outlined in the randomization Standard Operating Procedure under “Study tools”.

Blinding

This study uses behavioural interventions. Participants and most study staff are not blinded to the intervention assignment. However, both baseline and post-intervention questionnaire administration will be conducted by research assistants who will not be made aware of the treatment assignment of participants.

Methodology

Study Interventions

Docu-drama pilot test-run: Participants assigned to this group meet once during the intervention. Participants will be asked to watch, in the group setting, a two-episode drama, each lasting 15 minutes. The docu-drama on blood donation will address their concerns for donating blood again and address common donor fears. This will be followed by a one- hour discussion. The meeting will also address common donor fears. The meeting will be facilitated by two project team members who will moderate discussions, record attendance, and make notes on discussions and outcomes. Participants also receive standard National Blood Service Ghana (NBSG) communications for first-time donors (see below). The docu-drama design is subject to change in response to objective 1.

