Below are a number of statements relating to the participant's intent to donate blood. Read each statement to the participant, and have them indicate where they fall on the scale from 1 to 5.

1. I plan to donate blood in the next 4 months

Strongly Disagree 1 2 3 4 5 Strongly Agree

2. How likely is it that you will donate blood in the next 4 months?

Very Unlikely 1 2 3 4 5 Very Likely

3. I will donate blood in the next 4 months.

[figure not shown]
Very Unlikely 1 2 3 4 5 Very Likely

Signature: _____

Date: _____

7. Case Report Form for participants enrolled in the RCT of the study after randomization

[figure not shown]
Baseline B

Participant ID:	Form Date: (example: 01-APR-2021)	Participant 3-letter code:	Bloodsafe Logo Placeholder
	Form Date: (example: 01-APR-2021)  Day Month Year	Participant 3-letter code: 	Site: 01 Korle-Bu Bld Bank 02 Korle-Bu Maternity 03 Pentecost Hospital 04 LEKMA Hospital 05 Maamobi Polyclinic 06 Accra Shopping Mall 07 Mobile Unit

Complete this form immediately after randomization for all participants enrolled in the RCT of the C-CAD study.

A. Randomization

(example: 01-APR-2021)

1. Date of participant randomization: 

2. Indicate which arm of the study the participant is in. Follow the instructions listed for the arm.

- 1 Control
 2 WhatsApp

B. Intention of Using the Intervention

Yes No I don't know

1. I intend to use WhatsApp to discuss blood donation in the next 6 months

1 0 2

2. I intend to use WhatsApp to discuss blood donation as often as possible

1 0 2

3. I expect my use of WhatsApp to discuss blood donation to continue in the future

1 0 2

Items C, D, and E have a number of statements related to the acceptability, feasibility, and cultural appropriateness related to potential use of WhatsApp for blood donation education. Read each statement to the participant, and ask them to respond "Yes", "No", or "I don't know" to each statement.

C. Acceptability

Yes No I don't know

1. Using WhatsApp for promoting blood donation among first-time donors **is appealing**

1 0 2

2. Using WhatsApp for promoting blood donation among first-time donors **seems fine with me**

1 0 2

3. I have **no objection** to using WhatsApp for promoting blood donation among first-time donors

1 0 2

D. Feasibility

Yes No I don't know

1. Using WhatsApp for promoting blood donation among first-time donors seems **practical**

1 0 2

2. Using WhatsApp for promoting blood donation among first-time donors seems **possible**

1 0 2

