10. I feel disconnected from the world around me when viewing a docu-drama	1 	2 	3 	4 	5 
11. I don't feel related to most people when viewing a docu-drama	1 	2 	3 	4 	5 
12. I don't feel I participate with anyone or any group while viewing a docu-drama	1 	2 	3 	4 	5 

Signature: _____

Date: _____

9. Case Report Form for reporting participant death

Death

Participant ID:

Date of Death:
(example: 01-APR-2021)

		2	0	2	
Day	Month	Year			

Participant
3-letter code:

--	--	--

Bloodsafe Logo
Placeholder

01 Korle-Bu Bld Bank
02 Korle-Bu Maternity
03 Pentecost Hospital
04 LEKMA Hospital
05 Maamobi Polyclinic
06 Accra Shopping Mall
07 Mobile Unit

Site:

--	--	--

1. Record the primary cause of death.

- Enter only one cause (medical condition)
- Be as specific as possible
- DO NOT abbreviate
- DO NOT enter terminal events such as cardiac arrest, respiratory arrest, or ventricular fibrillation without showing the etiology

2. Where did death occur?

- 1 Home
- 2 Hospital
- 3 Other, specify: _____
- 4 Unknown

3. Are medical records available for this death, in the event that additional information is requested?

- 0 No
- 1 Yes

4. Provide a brief summary of events related to the death (if known):

--

Signature: _____

Date: _____

10. Case Report Form for participants enrolled in the RCT of the study attending the Month 6 visit

Month 6

Participant ID:	Form Date: (example: 01-APR-2021)	Participant 3-letter code:	Site:	Bloodsafe Logo Placeholder
	 Day  Month  2  0  2  Year			01 Korle-Bu Bld Bank 02 Korle-Bu Maternity 03 Pentecost Hospital 04 LEKMA Hospital 05 Maamobi Polyclinic 06 Accra Shopping Mall 07 Mobile Unit

Complete this form for participants enrolled in the RCT of the C-CAD study attending the Month 6 visit.
Indicate which arm of the study the participant is in. Follow the instructions listed for the arm.

- 1 Control
2 WhatsApp

A. Knowledge

What follows are a number of statements related to the participant's knowledge about donating blood.

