E. Demographics (continued)

12. What is your ethnic background?

- 1 Akan
- 2 Ewe
- 3 Dagbani
- 4 Ga/Dangbe
- 5 Hausa
- 6 Other, specify: _____

13. Do you belong to a religious faith?

- 1 Yes, Christian
- 2 Yes, Moslem
- 3 Yes, Traditionalist
- 4 Yes, Other, specify: _____
- 5 No

Signature: _____ Date: _____

16. Participation Withdrawal Form

Withdrawal

Participant ID:

Date of withdrawal:

(example: 01-APR-2021)

- - 0 2

Day

Month

Year

Participant
3-letter code:

Bloodsafe Logo
Placeholder

Site:

01 Korle-Bu Bld Bank
02 Korle-Bu Maternity
03 Pentecost Hospital
04 LEKMA Hospital
05 Maamobi Polyclinic
06 Accra Shopping Mall
07 Mobile Unit

Complete this form if a participant has actively (verbally or in writing) withdrawn consent or if the participant is withdrawn by the PI from the C-CAD study.

A. Withdrawal

1. Indicate the type of withdrawal (mark only one):

- 1 Participant actively withdrew consent from all aspects of the C-CAD study
2 Administrative withdrawal

2. The participant requested destruction of the following (mark all that apply):

- 1 All participant recordings
2 All participant data
3 N/A (The participant did not request destruction of data or recordings)

3. Reason for withdrawal:

- 1 Participant preference
2 Staff/PI request
3 IRB/sponsor request
4 Other; specify: _____

Staff person completing this form (please print): _____

Signature: _____

Signature indicates a withdrawal has been verified with site and all necessary documentation is available.

17. SOP: Randomizing participants into study groups for the pilot RCT of WhatsApp and control

BLOODSAFE: Standard Operating Procedure

Randomizing participants into study groups for the pilot RCT of WhatsApp and control		Version 0.3 15 Feb 2021
---	--	-----------------------------------

Revision history		
Version	Date	Description

1. Purpose

The purpose of this standard operating procedure (SOP) is to describe how to use the randomization application for the pilot RCT of WhatsApp and control for the *Community-Based Communication Approaches for Blood Donation in Ghana-Pilot Study* (C-CAD) study. Participants are allocated with a 1:1 ratio to WhatsApp or control stratified by one of two donor types (e.g., Voluntary non-remunerated donor or Family/replacement donor) using the web-based application described in this SOP. Participants will be randomized after the consent and screening process immediately following completion of Baseline A case report form (CRF).

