2. Scope and responsibilities

Allocation into study groups for C-CAD will be performed using the randomization application tool on the study website. The protocol principal investigator determines who will be given randomization privileges. Only the research assistants (RAs) assigned to C-CAD randomization as listed in the delegation log for this protocol will have access to the randomization application tool. The web-based application has been designed so that the upcoming intervention assignment is concealed from the study staff prior to the randomization outcome.

[figure not shown]
3. Accessing the randomization application on the website.

Only study RAs with randomization permissions for C-CAD will be able to see the link for the randomization application tool. Each study RA with permissions must complete the training requirements prior to randomizing a C-CAD participant. Training includes at least 3 practice randomizations using a test website and the training must be documented by the data coordinating center.

The randomization application tool, [Randomization Application \(Pilot RCT of WhatsApp and Control\)](#), is located under the C-CAD specific protocol page below [Documents and Downloads](#) (see Figure 1). If you do not see the randomization application, you do not have permissions to randomize participants for C-CAD.

BLOODSAFE: Standard Operating Procedure

Randomizing participants into study groups for the pilot RCT of WhatsApp and control		Version 0.3 15 Feb 2021
--	--	----------------------------

The screenshot shows the BLOODSAFE website interface. On the left, a sidebar lists 'Research Projects in' with 'Ghana' selected, which is highlighted with a red circle. Under 'Ghana', the 'C-CAD' button is also highlighted with a red circle. The main content area is titled 'Ghana: C-CAD' and describes a pilot randomized controlled trial for increasing the blood donor pool in Ghana. It includes details about the study design, principal investigators, and Clinicaltrials.gov identifier. Below this, a 'Documents and Downloads' section is shown, with the 'Randomization Application (Pilot RCT of WhatsApp and Control)' link highlighted with a red circle.

Figure 1: Location of randomization application on the BLOODSAFE website.

4. Performing individual random group allocation during an onsite blood donation visit.

4.1. Determine the type of donor for this blood donation visit using the study definitions.

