The participant with PID **9111-012-2** has been randomized to the **WhatsApp** arm of the study.

[Randomize another PID](#)

C-CAD randomization assignment

The participant with PID **9111-013-0** has been randomized to the **Control** arm of the study.

[Randomize another PID](#)

Figure 4: Example of randomization application outcomes screen for two different PIDs.

4.5. Record the date, randomization stratum, and outcome of the randomization outcome on the Baseline B CRF (C-CAD BASB) Section A. Randomization (see Figure 5).

Baseline B

Participant ID:
	
Form Date: (example: 01-APR-2021)
 
 
 Day	Month	2	0	2	Year	
 
	Day	Month	2	0	2	Year	
Participant 3-letter code:

Day	Month	2	0	2	Year			
								

Complete this form immediately after the Baseline A form for all participants enrolled in the pilot RCT of WhatsApp and Control.

A. Randomization

1. Date of participant randomization:

Day	Month	2	0	2	Year
-----	-------	---	---	---	------
2. Indicate which randomization stratum the participant is in
 - Voluntary non-remunerated blood donor
 - Family/replacement donor
3. Indicate which arm of the study the participant is in.
 - Control
 - WhatsApp

Figure 5: Complete Section A. Randomization with the date, stratum and randomization application outcome.

18. Phone Interview Guide

Title: Community-based communication interventions for increasing the blood donor pool in Ghana: a randomized controlled trial

Phone Interview Guide

Introduction should be brief, clearly identifying the caller, caller's institution and referring to the invitation to participation. In asking to speak with the intended participant, the actual nature of the call should not be disclosed to a third party. For instance, it is enough to say "*I would like to speak with... in relation to having scheduled a phone interview earlier about blood donation*".

A. STRATEGIES FOR INCREASING PHONE INTERVIEW PARTICIPATION

Hangs up before hearing reason for survey. Call back!

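### The Month 6 form has the arm marked before any question is asked, which conflicts with the protocol's statement that post-intervention questionnaires are given by assistants unaware of assignment

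*Combined protocol and SAP*

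**What the plan says.** **The masking statement.** The Blinding section accepts that "Participants and most study staff are not blinded to the intervention assignment". It then makes an exception for data collection: the baseline and post-intervention questionnaires are to be "conducted by research assistants who will not be made aware of the treatment assignment of participants".

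**The Month 6 form (Study Tools, item 10).** Above section A, the person completing the form is told: "Indicate which arm of the study the participant is in. Follow the instructions listed for the arm". Boxes for Control and WhatsApp follow. The scales come next and are read aloud to the participant. Section P, on return donation attempts, comes last. The follow-up section says that this assessment is done by telephone.

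**The Baseline B form (Study Tools, item 7).** Its heading says: "Complete this form immediately after randomization for all participants enrolled in the RCT of the C-CAD study". Section A carries the same arm item, ahead of the scales. Step 4.5 of the randomization SOP (Study Tools, item 17) tells staff: "Record the date, randomization stratum, and outcome of the randomization outcome on the Baseline B CRF".

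**Staff roles.** Under the SOP's scope and responsibilities, access to the randomization tool is limited: "Only the research assistants (RAs) assigned to C-CAD randomization as listed in the delegation log" can use it. The WhatsApp pilot RCT section names a research assistant as content mediator of the group.

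**The concern.** Interviewer masking is the only masking the protocol claims once allocation is known. The concealment described in the Randomization section and the SOP ends when the assignment is displayed.

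The secondary outcomes are answers to statements read out by an interviewer, on matters such as attitudes, intention and acceptability. An interviewer who knows the arm can affect tone, probing or recording, even without meaning to. If the form discloses the arm at the start of the call, the trial would report a safeguard that its own paperwork removes. The pilot is meant to inform the larger trial, so the same form could be carried forward.

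**Working it through.** No figure in the plan needs reproducing. The check sets the masking statement beside the forms and counts what lies below the arm field.

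**1. Does the statement cover Month 6?** Yes. The Month 6 form is the RCT's post-intervention questionnaire, and no reading of the Blinding section leaves it out.

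**2. What does the form require?** The arm is marked before section A. The form has one closing signature line and names no second person to complete the arm field. It tells the user to follow arm-specific instructions, but none are printed. The documents describe no detachable page, covered field or other masking step. Because the assessment is by telephone, a caller completing the form as printed must be told the arm or ask for it.

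**3. How much follows the arm field?**

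- Scales repeated from Baseline A (sections A to F): knowledge 12, beliefs 5, attitudes 6, subjective norms 6, perceived behavioural control 5, intention 3. Sum: 12 + 5 + 6 + 6 + 5 + 3 = 37.
- Scales repeated from Baseline B (sections H to O; there is no section G): intention of use 3, acceptability 3, feasibility 4, cultural appropriateness 3, usefulness 3, ease of use 3, relatedness 9, connectedness 12. Sum: 3 + 3 + 4 + 3 + 3 + 3 + 9 + 12 = 40.
- Total: 37 + 40 = 77 items in 6 + 8 = 14 sections. Section P follows.

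**4. How much of that bears on a listed secondary outcome?** Knowledge and beliefs (12 + 5 = 17 items) are not in the Secondary Outcomes list, although the Secondary Objectives name both as potential mediators. That leaves 77 − 17 = 60 items, counting both relatedness and connectedness toward intervention relatedness. The list for WhatsApp and control has 6 + 4 + 1 = 11 outcomes. Table 1 does not mark intention of use at 6 months, but the follow-up text and section H of the form include it. So 11 outcomes are affected at Month 6 by the text and form, or 10 by Table 1.

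**5. Is the arm field needed for analysis?** No. SOP steps 4.2 to 4.4 show the application taking the participant ID and returning the assignment for that ID. The arm can therefore be linked afterwards without loss.

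**6. Baseline A and Baseline B.** Baseline A is completed before randomization and has no arm field, so timing masks it. Baseline B is completed after randomization and shows the arm. Whether that breaches the Blinding section depends on what baseline means there. The Randomization section, just before it, uses baseline assessment for what precedes randomization. Table 1 and the follow-up text also call the post-randomization form baseline. The text does not settle it.

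**The case against.** **The masking statement already separates the roles.** By its own terms, it excludes anyone who knows the allocation, so neither the randomizing assistant nor the WhatsApp mediator should make Month 6 calls. This stands. A reader might infer that these people do give the questionnaires, or that assessors were unmasked in practice. The documents do not support that: the delegation log is not among them, and any overlap is unknown. Separate roles still leave the arm box on the caller's form.

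**The form does not say who marks the arm.** True. That the interviewer does so is an inference from the layout, the read-aloud instructions and the single signature line. Nothing in the documents points to anyone else.

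**Baseline B may be consistent.** This also stands. A reader might conclude that Baseline B contradicts the protocol too, so that the seven outcomes first measured there lose masking at both time points. That holds only if baseline in the Blinding section includes Baseline B. What can be said is that those items are collected after allocation on a form that shows the arm.

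**The form versions are not settled.** The Baseline B shown in SOP Figure 5 has a stratum item that the form in Study Tools item 7 lacks, and it omits the sentence about arm-specific instructions. It still records the arm.

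**The consequence is limited.** Participants know their arm and report on themselves. The pilot acknowledges low power, and secondary analyses are not centred on significance. Focus groups add a second source on acceptability, feasibility and cultural appropriateness. All of this lowers the stakes, but it does not make the form agree with the statement.

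**Conclusion.** The point holds for Month 6. The Blinding section and the Month 6 form cannot both be followed as written, if the interviewer completes the whole form, as its layout implies. The extent is 77 of 77 scale items and section P. Of the 77, 60 bear on listed secondary outcomes and 17 do not.

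The primary outcome is partly protected, because reported donor return is cross-checked with SZBC donor records. The count of items below a checkbox measures exposure, not bias. The documents give no basis for the size or direction of any interviewer effect.

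For Baseline B, the finding is an ambiguity to resolve, not a proven contradiction.

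**What to change.** 1. **Month 6 form.** Delete the arm field and the sentence about arm-specific instructions. Have the data coordinating center merge the arm by participant ID from the randomization application. State that Month 6 callers receive no allocation information. Under the Blinding section, this already rules out the WhatsApp mediator and the randomizing assistant as callers.
2. **Baseline B.** Either amend the Blinding section to say that Baseline A is masked by timing and that Baseline B is collected after allocation on a form showing the arm, or move arm and stratum to a separate randomization form and change SOP step 4.5 to match.
3. **Form versions.** Reconcile the Baseline B form in Study Tools item 7 with the one in SOP Figure 5.

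The cost is minor form edits, a sentence or two in the Blinding section and, if the separate form is chosen, one short form and one SOP step. No visit or scale changes. Staff who know the allocation are unavailable for Month 6 calls. Masking stays imperfect, because participants may reveal their arm during the call.
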